#### **Consent process**

The patients will be given the study information by their obstetrical provider in the third trimester once patient has been identified as meeting the inclusion criteria. If interested, the obstetrical provider will notify study personnel and personnel will obtain written consent at subsequent visits (i.e when presenting for pre-operative labs at the Martha Stewart Laboratory). Alternatively, patients will provide informed consent online and over phone/zoom to facilitate consent process while maintaining social distancing.

#### **Product storage and preparation**

The device will be stored in the locked office of one of the research personnel and will only be handles by the research team until randomization is performed and the patient is allocated to the treatment arm. Only at that time would the research personnel go into the locked office and obtain the suture material for the subject. The material would be then handed off with sterility to the scrub tech who would provide the suture to the surgeon during the procedure

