**General Design:** This is a prospective, randomized controlled trial evaluating whether using a barbed suture to close a C-section incision can reduce blood loss. Patients undergoing C-section will be randomized with equal allocation to a barbed suture or a standard antimicrobial suture. The primary outcome is quantification of blood loss (QBL). At Mount Sinai Hospital, QBL is calculated by Triton AI which captures sponge and canister images to accurately monitor blood loss in real time. Differences between the groups will be assessed using a 0.05 level Wilcoxon rank-sum test. Secondary outcomes include time for hysterotomy closure, need for additional hemostatic sutures, rate of endometritis/SSI (superficial wound infection, deep wound infection, and endometritis) within 6 weeks postpartum, use of hemostatic agents, and differences in pain which will be assessed by a telephone screening in the days following delivery. The Mann-Whitney test will be used to compare continuous outcomes between the barbed suture and antimicrobial suture groups. Continuous secondary outcomes include time for hysterotomy closure (in minutes), and difference in pain between post-surgery day 1 and day 14. The Chi-square test or Fisher's exact test (as appropriate) will be used to compare the incidence rate of binary outcomes between the two patient groups. Binary secondary outcomes include need for additional hemostatic sutures (Y/N), endometritis or surgical site infection (SSI) within 6 weeks of surgery (Y/N), and use of hemostatic agents (Y/N). **Inclusion criteria** (1) those undergoing an elective scheduled cesarean delivery at  $\geq 37$  weeks' gestation, (2) those in labor requiring cesarean delivery for usual obstetrical indications, or (3) those who failed a trial of labor after a previous cesarean delivery at Mount Sinai Hospital ages 18-64. **Exclusion criteria include**, multifetal gestations, placenta previas, and patients with a known coagulopathy (DIC, Von Willebrands Disease, etc). Also excluded are patients with IAI, patients on magnesium sulfate, placenta abruption, and PAS.

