**Sample Size:** Sample size is based on a two-sided, equal variance T-test. Since the distribution of QBL is non-normal, the calculation was inflated by 15% to ensure adequate power for the nonparametric Wilcoxon rank-sum test as recommended by Lehmann (5). Based on data from C-section patients seen at Mount Sinai from 2018-2019, the distribution of QBL is assumed to have a mean of 534 and a standard deviation of 371. (Figure 1).

*Figure 1. Distribution of QBL in C-Section Patients at Mount Sinai from 2018-2019*

Assuming each group has a standard deviation of 371 and the control group has a mean QBL of 534, a sample size of 226 patients (113 in each group) provides ~85% power to detect a 30% decrease in mean QBL between the groups at the 0.05 significance level. Sample size for alternative effect sizes are tabled below. 300 sutures are requested by the investigators to standardize a double layer closure for all patients as is the standard of care for most Obstetricians (113 patients in the barbed suture arm, double layer would require 226 suture, we are requesting 452 suture so extra suture is available should additional hemostatic sutures be needed.

Power	Alpha	Mean QBL in Control Group	Mean QBL in Experimental Group	Standard Deviation in Both Groups	Absolute Difference of Means	Relative Difference of Means	Group N	Total N
0.85	0.05	534	267	371	267	50%	42	84
0.85	0.05	534	320.4	371	213.6	40%	65	130
0.85	0.05	534	373.8	371	160.2	30%	113	226
0.85	0.05	534	427.2	371	106.8	20%	251	502

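### The study suture leaves a locked office only after allocation, at a time the plan does not fix, so pre-closure QBL may be exposed to knowledge of the arm, or a mid-operation fetch may chiefly penalise the barbed arm

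*Combined protocol and SAP*

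**What the plan says.** Under Product storage and preparation, the device stays in the locked office of one member of the research team until the patient has been randomized. Then: "Only at that time would the research personnel go into the locked office and obtain the suture material for the subject". It is next "handed off with sterility to the scrub tech who would provide the suture to the surgeon during the procedure". This fixes an order (randomize, fetch, hand over) but no time relative to incision, delivery or closure.

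Three other places bear on the point.

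- **Eligibility (General Design).** Unscheduled cases are included: "those in labor requiring cesarean delivery for usual obstetrical indications".
- **Primary outcome (General Design).** QBL is captured in real time from sponge and canister images. No start, stop or restriction to loss after closure begins is given.
- **Suture supply (Sample Size).** The request is counted on the 113 barbed-arm patients only (two sutures each, 226, raised to 452 for spares). No control suture is requested, and the comparator is described as standard.

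The documents give no allocation-concealment method, no statement on blinding, no backup-stock rule, and no rule for analysing patients who do not receive their allocated suture.

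**The concern.** The randomized treatment acts only from uterine closure onward, but QBL as written may include everything lost before that. The best moment to reveal the arm is therefore just before closure, with both sutures already at hand. The storage rule works against this, because the study suture cannot be in the room until the arm is known.

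Two things are at stake. The first is bias: if the arm is known during incision, delivery and placental removal, open-label behaviour can alter loss that the suture cannot influence, and that loss is counted in the primary outcome. The second is dilution or delay: if the fetch takes place mid-operation, or the suture does not arrive in time, the barbed arm chiefly bears the consequence. Closure with standard suture pulls the arms together. Waiting for the suture could add loss in one arm.

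**Working it through.** **1. Timing, taken both ways.**

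- *Allocation before incision.* At least the research staff know the arm before any blood is lost, and the operating team may too. Pre-closure QBL is exposed.
- *Allocation after incision.* The fetch occurs during the operation. Delay, or closure with standard suture, becomes possible, and more so in in-labor cases.

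The text does not say which applies. Each carries a risk that pre-positioned sutures would reduce.

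**2. Which arm depends on the fetch.** Study stock is counted for the barbed arm only and the comparator is called standard, so the natural reading is that the control suture comes from routine supply. Its storage is not described, so the burden falls chiefly, not provably only, on the barbed arm.

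**3. The plan's sample size, reproduced.** Inputs from General Design and Sample Size: "Differences between the groups will be assessed using a 0.05 level Wilcoxon rank-sum test"; "Sample size is based on a two-sided, equal variance T-test"; "Assuming each group has a standard deviation of 371 and the control group has a mean QBL of 534"; "the calculation was inflated by 15% to ensure adequate power for the nonparametric Wilcoxon rank-sum test".

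- Difference = 0.30 × 534 = 160.2; standardized, 160.2/371 = 0.432.
- The two-sided t-test at 0.05 and 85% power needs 97.3, rounded up to 98 per arm.
- 98 × 1.15 = 112.7, rounded up to 113 per arm, 226 in total.

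This matches the stated figure: "a sample size of 226 patients (113 in each group) provides ~85% power to detect a 30% decrease in mean QBL between the groups". Removing the 15% rank-test allowance leaves 113/1.15 = 98.3 effective patients per arm and power of 85.4%.

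**4. Dilution from one-way non-adherence.** Let f be the share of the barbed arm closed with standard suture. The documents give no value, so f is an assumption. With patients analysed as randomized and the SD held at 371, the difference becomes 160.2 × (1 − f). Power is from the noncentral t at 98.3 per arm. The last column repeats step 3, with rounding up before and after the factor 1.15.

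| f (assumed) | Difference | Power at 113 per arm | Per arm for 85% |
|---|---|---|---|
| 0% | 160.2 | 85.4% | 113 |
| 5% | 152.2 | 81.6% | 108 × 1.15 = 124.2 → 125 |
| 10% | 144.2 | 77.4% | 120 × 1.15 = 138 |
| 20% | 128.2 | 67.3% | 152 × 1.15 = 174.8 → 175 |

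The 15% inflation is for the rank test, so nothing in the plan absorbs this loss.

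**5. Effect of arm knowledge on type I error (illustrative).** Assume that 60% of mean loss occurs before closure and that knowing the arm shifts it by 5% in one direction: 0.05 × 0.60 × 534 = 16.0 (QBL taken to be in mL). With no true suture effect:

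- SE = 371 × √(2/113) = 49.4; 16.0/49.4 = 0.32.
- P(|Z + 0.32| > 1.96) = 0.051 + 0.011 = 6.2%.
- On the 98.3-per-arm basis of step 4, SE = 52.9 and the result is 6.1%.

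So the error rate is about 6% instead of 5% on either basis.

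**The case against.** The strongest reply is that the storage paragraph fixes only a sequence. It gives no office location, distance or clock time, and it has the surgeon receive the suture during the procedure. A reader might infer that allocation must be made and known to the operating team before surgery. The text does not support that: randomization and the fetch could start at or after incision, and an earlier allocation could be withheld from the surgeon until hand-off. This stands.

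A reader might also infer that only the barbed arm can miss its suture, and that an absent keyholder means closure with standard suture. Neither is stated. Control-arm deviations are not ruled out. The documents do not say who randomizes; if the same staff randomize and fetch, their absence means a patient who is never randomized, which is a lost enrolment and not a crossover. This stands too, and under that arrangement much of the dilution would disappear.

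On size, the image-based QBL system limits subjective estimation, and the shift in step 5 has no source in the documents. Larger shifts are hard to reconcile with the plan. A shift of 27 (5% of the full 534) would require all loss to precede closure, leaving nothing for the suture to reduce and contradicting the 30% effect. Even the 60% case leaves 0.40 × 534 = 213.6 after closure, so a reduction of 160.2 would be 75% of it. The type I error figure should therefore be read as an order of magnitude only.

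What the reply does not do is rescue the rule: neither timing is free of risk, and the plan does not choose between them.

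**Conclusion.** The concern holds in a limited form. The storage rule, with unspecified randomization timing and no QBL window, makes two problems possible: knowledge of the arm while pre-closure loss accrues, or a mid-operation fetch whose failures fall chiefly on the barbed arm. It does not prove that either will happen.

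Under assumed one-way non-adherence of 5%, 10% or 20%, power falls from about 85% to about 82%, 77% or 67%. These figures rest on analysis as randomized, full loss of benefit in the affected patients and an unchanged SD. The bias figure, about 6% type I error for an assumed 16 mL shift, is illustrative only. The sample size of 226 is correctly derived and is not in dispute. The change is worth making because it is cheap and helps under either timing, with medium confidence about how much it matters in practice.

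**What to change.** Rewrite the storage and hand-off paragraph along these lines:

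- For every consented patient going to cesarean, a sealed barbed pack and the standard suture are both in the operating room before incision.
- Allocation is concealed (sealed opaque envelope or an equivalent system) and revealed only when uterine closure is about to start. REDCap is described under Data handling and storage for data entry, so if it is to hold the allocation, the plan should say so.
- Unopened packs are logged and returned to stock.

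This needs no extra patients or staff and no change to the analysis. The costs are pack logging, one brief extra step just before closure, and slightly looser device storage than a locked office. Two limits remain. Someone must still place the pack before incision in urgent in-labor cases, so the availability problem is moved earlier and eased, not abolished. And the operating team is unblinded from closure onward, so open-label influence on later loss is untouched.

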#### **Safety assessments**

This research involves less than minimal risk. To mitigate the risk of breach of confidentiality and ensure confidentiality, the following system will be adhered to: when subjects are enrolled in this study, they will be assigned a unique identification code. Corresponding medical record numbers for each code (keycode will be stored in a password locked documentation the MFM servers that can be accessed only by members of the research team. At the conclusion of the data extraction, the outcome variable will be assessed and the key codes to the medical record number will no longer be necessary and that information will be permanently erased from the key code file. Electronic data with identifiers will be encrypted according to Data Security Standards.

